The primary safety endpoint is defined as the proportion of subjects experiencing a MAE within 30 days post-implantation. MAEs include the occurrence of any of the following events:

- All-cause mortality
- Bowel ischemia
- Myocardial infarction
- Paraplegia
- Procedural blood loss ≥ 1000 cc
- Renal failure
- Respiratory failure
- Stroke

Detailed definitions of MAEs are provided in Appendix L.2.

C.2.1.2 Primary Effectiveness Endpoint

Technical success at the index procedure (as assessed intra-operatively) is defined as successful delivery and deployment of the Endurant Evo AAA Stent graft system in the planned location and with no unintentional coverage of both internal iliac arteries or any visceral aortic branches and with successful removal of the delivery system

C.2.2 Secondary Endpoints

The following secondary endpoints will be evaluated:

- All cause-mortality within 30, 183, and 365 days
- Aneurysm-related mortality within 30, 183, and 365 days
- Secondary procedures to correct Type I and III endoleaks within 30, 183 and 365 days
- Secondary endovascular procedures within 30, 183 and 365 days
- Serious adverse events within 30, 183 and 365 days
- Aneurysm rupture within 30, 183 and 365 days
- Conversion to open surgery within 30, 183 and 365 days
- Major adverse events within 183 and 365 days
- Stent graft migration at 12-month follow-up visit (as compared to 1-month imaging)
- Aneurysm expansion > 5 mm at 12-month follow-up visit (as compared to 1-month imaging)
- All endoleaks based on imaging findings at 1- month, 6-month and 12-month visits
- Stent graft occlusion based on imaging findings through 6 months and 12 months

Device deficiencies based on imaging findings through 6 months and 12 months Secondary endpoints will be assessed at annual follow-up visits until 5 years post-implantation Detailed definitions for secondary endpoints are provided in Appendix L.2.

C.3 Study Hypothesis

The Endurant Evo International Clinical Trial is not hypothesis driven; all endpoints will be analyzed descriptively.

Endurant Evo is a next generation abdominal low profile stent graft system on the Endurant product platform. The safety and performance of the commercially available Endurant and Endurant II devices have been well established. As such, this trial is not designed to make a statistical comparison, but rather to collect data demonstrating that the Endurant Evo system performs as expected clinically.

C.4 Study population

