Screening CT/MRA images will be sent to a core lab to assess the anatomical inclusion/exclusion requirements. An Independent Physician Reviewer (IPR) will review screening CT/MRA images to determine eligibility. Approval by the IPR must be obtained prior to a subject's enrollment in the study. The decision of the IPR will be communicated to the investigational site by the Sponsor. Those subjects who sign and date the Informed Consent, meet all study eligibility criteria, and are approved by the IPR will be eligible for enrollment. Subjects that are not approved by the IPR are considered screen failures and will not be enrolled in the study.

Subjects who do not qualify for enrollment will be documented as ineligible on the Screening and Enrollment log.

Enrollment:

Those subjects who sign and date the informed consent document, meet all of the study eligibility criteria, and are approved by the IPR will be eligible for enrollment into the Endurant Evo International Clinical Trial. The subject will be considered to be enrolled when arterial access has been established with an attempt to introduce the Endurant Evo AAA stent graft.

Enrolled subjects will be documented on the Screening and Enrollment Log. Subjects who are enrolled, but not implanted with the device will be followed through the 1 month follow-up only.

The investigator will maintain a log of all subjects screened and enrolled in the clinical study, assigning an identification code linked to their names, alternative subject identification or contact information.

F.2 Implant and Follow up

F.2.1 Index Procedure

All investigators will read, understand and be trained to the Endurant Evo AAA stent graft system Instructions for Use (IFU) prior to initiation of the procedure. The IFU is packaged with the device and must be followed for implantation of the stent graft system.

Identification and/or serial numbers for all investigational components of the Endurant Evo AAA stent graft system used or opened during the index procedure will be recorded.

Adverse event assessment should be done for all subjects as of the moment the subject is considered to be enrolled in the study.

F.2.1.2 Treatment failure

Inability to implant the Endurant Evo AAA stent graft system following arterial access due to deployment issues or entrapment of the delivery system will be considered a treatment failure. These subjects will be followed through the 1-month follow-up time point and then exited from the study.

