If a primary conversion to open repair is required during the index procedure, then the subject will be followed for 1 month, at which time the subject will be exited from the study.

After exiting the study, subjects will be followed as per their institutional standard of care.

F.2.2 Hospital Discharge

The following assessments and procedures will be performed and respective data will be collected at hospital discharge:

- Adverse event assessment
- Duration of intensive care unit stay after index procedure (in hours)

F.2.3 Follow-Up Visits and Procedures

Each subject will have required post-implantation follow-up visits at 30-days, 6-month, 12-months, and annually thereafter until 5 years post implantation. Follow-up visits and associated timeframe windows are summarized in Table F-1. Given the DDs with SAE potential that have occurred within the Endurant Evo trials, the Data Monitoring Committee (DMC) has made additional imaging surveillance recommendations, beyond the required follow-up in the protocol. The additional imaging surveillance recommendations are provided, under separate cover, in the most recent DMC Surveillance and Management letter that has been provided to each investigational site.

Table F-1: Post-Implantation Follow-Up Schedule and Windows

Follow-Up Visit	Window Start Day	Target Day	Window Close Day
1 Month (\pm 15 days)	15	30	45
6 Month (\pm 30 days)	153	183	213
12 Months (-30/+56 days)	335	365	421
24 Months (\pm 56 days)	675	731	787
36 Months (\pm 56 days)	1040	1096	1152
48 Months (\pm 56 days)	1405	1461	1517
60 Months (\pm 56 days)	1770	1826	1882

At all required follow-up visits subjects will undergo the following assessments:

- Physical Exam (to be reported in FUP eCRF until 24 months only)
- CT/MR with contrast and non-contrast (2 cm above the origin of the celiac artery through the bifurcation of the femoral arteries). At the 6 month follow-up visit: Duplex Ultrasound can be performed if abdominal CT/MR with contrast is not hospital standard of care.
- Abdominal X-ray (4-view, KUB)
- EQ5D questionnaire (until 12 month F/U only)
- Adverse event assessment
- Concomitant Medication (to be reported in FUP eCRF until 24 months only)

If a CT/MR is acquired at discharge (or before Day 15) due to medical necessity, or at the discretion

of the investigator, it may be used to meet the 1-month follow-up visit CT/MR requirement and acquisition of an additional 1-month CT/MR with contrast would not be required.

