Abdominal X-rays should be completed via a four-view kidney, ureter, bladder (KUB) X-ray. Posterior/anterior (PA) and lateral images are recommended for visualization of the stent graft. Ensure the entire device is captured on images for assessment.

If conversion to open repair is required during the follow-up period, then the subject will be followed for 30 days after the conversion, at which time the subject will be exited from the study. Please refer to Device Explant and Returned Procedures/Products section, located in E.6.3 of the protocol.

F.3 Data Collection Requirements

Clinical data will be collected preoperatively to establish eligibility, at baseline, during the index procedure, throughout the hospital stay, and postoperatively at the required (and any interim imaging) follow-up visits described in Section F.2. The data collection schedule is summarized in Table F-2. Imaging source data will be sent to the Core Lab for analysis up to the 60-month follow-up visit. Any interim imaging of the stent graft region but not linked to a study visit should be sent to the Core Lab (e.g. imaging performed as standard of care beyond the protocol required time points and/or when performed further to any issue observed at previous imaging Follow-up). This also includes Interim imaging performed, as recommended per the most recent DMC Surveillance and Management letter. All images taken from the stent graft region must be assessed by the site. Any findings that meet the requirements in the flowchart (Appendix L.5) must be reported on the applicable eCRF. Study data will be collected using electronic case report forms (eCRFs) as described in Section G.1. Clinical investigators must electronically review and approve all eCRFs. The monitoring strategy will be defined in the monitoring plan.

Table F-2: Data Collection Schedule

DATA	Screening/ Baseline	Index Procedure	Hospital Discharge	1-Mo. FU (±15 days)	6-Mo. FU (±30 days)	12-Mo. FU (-30/+56 days)	2 Yr. FU (±56 days)	3-5 Yr. FU (±56 days)
Informed consent	✓							
Inclusion / Exclusion criteria	✓							
Physical examination	✓			✓	✓	✓	✓	
Medical history	✓							
Current health status and risk factors	✓							
Laboratory tests at screening:Creatinine, INR ^d	✓							
Device and procedure information		✓						
Implant adjunctive procedures		✓						
Hospital discharge information			✓					
Medications	✓			✓	✓	✓	✓	
Adverse event assessment		✓	✓	✓	✓	✓	✓	✓
EQ5D questionnaire	✓			✓	✓	✓		
IMAGING								

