After study termination relevant medical records may be made available by the investigational sites for the treating physician per local laws and regulations if needed for further subject treatment. As per local law and regulation the trial investigator may be contacted by the treating physician in case of questions related to the study device and treatment.

G.4 Study close out

Prior to completion of study close out, all data must be entered and approved in the EDC system. Medtronic and/or its designees will notify the site of the intention to close the study. Remote study close out visits may be performed. The intent of these visits will be to assure the investigator's regulatory files are up to date and complete and that any outstanding issues from previous visits have been resolved. Medtronic will notify and inform the site(s) that all requirements have been met with a study closure letter.

If required, EC/IRB and/or regulatory authority will be informed by Medtronic about the study close out.

H DATA ANALYSIS AND REPORTING

Any deviations from this section will be described and justified in the final clinical study report, as appropriate.

H.1 Analysis of clinical data

All endpoints will be analyzed descriptively. In general, qualitative parameters will be described by their distribution frequencies; quantitative parameters will be described by their mean, standard deviation, minimum, maximum, median, and number of subjects with assessable data.

The survival from all-cause mortality over one year time or longer will be described by the Kaplan-Meier survival curve and the associated Kaplan-Meier estimate will be calculated along with its standard error using the Greenwood method.

For events such as AEs, deaths and secondary procedures, that can occur or are observed at any time during the study, no time window will be applied. For such events, an event that occurs "within 1 month or 30 days" is an event that takes place between Days 0 to 30, inclusive. Similarly, an event that occurs "within 12 months or 365 days" is an event occurring between Day 0 to Day 365, inclusive. Date of event onset will be used to determine when the event occurred. Day 0 is referring to the day of index procedure.

For image-based assessments, such as stent-graft endoleak, patency, and other observations, the following time windows will be applied for by-visit data summaries:

Table H-1: Time Windows for Statistical Analyses

Study Visit	Target Day	Time Window

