8.4. Analysis of the Primary Endpoints

For the primary endpoint, a one-sided 95% confidence interval based on binomial distribution will be constructed in addition to event count and frequency.

The analysis for the regulatory submission will take place when 40 subjects have been implanted with the study device for at least 30 days except that a subject expires early. Endpoints as defined in Section 5 will be analyzed for these 40 ITT subjects.

MAE Rate Calculation:

All MAEs will be adjudicated by the Clinical Event Committee (CEC) per protocol except for the procedural blood loss ≥ 1000 cc, which will be site reported at the index procedure. MAE rate will be calculated as follows (Table 2):

Table 2: MAE Rate Calculation:

MAE rate = $m/(m + k)$	Within 30 Days	Within 183 Days	Within 365 Days
$m = \text{No. of Subjects Who Had MAE(s)}$	No. of subjects who had at least one MAE with onset day from Day 0 to Day 30, inclusive.	No. of subjects who had at least one MAE with onset day from Day 31 to Day 183, inclusive.	No. of subjects who had at least one MAE with onset day from Day 184 to Day 365, inclusive.
$k = \text{No. of Subjects Who Had No MAE}$	No. of subjects who have been in study for at least 1 day and without an MAE.	No. of subjects who have been in study for at least 91 days and without an MAE.	No. of subjects who have been in study for at least 305 days and without an MAE.

If a subject is early terminated from the study, the last day that the subject has been seen will be the duration in study, which can be the day of last follow-up, last imaging taken, an AE reported, or withdrawal from the study. If a subject is still in the study, the duration in study will be the time from index procedure to the cut off day that the database is locked or data snapshot is taken.

Imaging based Event Rate Calculation:

Imaging assessment will be performed by site as well as the core lab. Assessments from the core lab will be analyzed separately from those by site. Imaging based event rate will be calculated using statistical analysis windows as follows (Table 3):

Table 3: Imaging based Event Rate Calculation:

Event rate = m/n	At 1 Month	At 6 Months	At 12 Months
$m = \text{No. of Subjects Who Had Event(s)}$	No. of subjects who had an event with scan day within the 1-month window.	No. of subjects who had an event with scan day within the 6-month window.	No. of subjects who had an event with scan day within the 12-month window.

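### The exit wording for enrolled but non-implanted subjects can be read to end follow-up as early as Day 15, and SAP Table 2 would still count them as MAE-free through Day 30

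*Protocol*

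**What the plan says.** Endpoint. Protocol C.2.1.1: "The primary safety endpoint is defined as the proportion of subjects experiencing a MAE within 30 days post-implantation". H.1 and SAP 8.1 fix the window: an event within 1 month or 30 days "is an event that takes place between Days 0 to 30, inclusive", dated by onset, with Day 0 the index procedure.

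Exit rules. There are four, and they are worded differently:

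- Enrolled but not implanted (F.1): "Subjects who are enrolled, but not implanted with the device will be followed through the 1 month follow-up only".
- Treatment failure, meaning deployment problems or an entrapped delivery system (F.2.1.2): "These subjects will be followed through the 1-month follow-up time point and then exited from the study".
- Primary conversion to open repair (F.2.1.2, F.7.5): "then the subject will be followed for 1 month, at which time the subject will be exited from the study".
- Secondary conversion (F.2.3, F.7.5): "then the subject will be followed for 30 days after the conversion, at which time the subject will be exited from the study".

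Visit timing. F.2.3 opens with "Each subject will have required post-implantation follow-up visits at 30-days". Table F-1 then gives the 1-month visit a target of Day 30 and a window from Day 15 to Day 45.

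Counting. Protocol H.1 and SAP 4.1 put every subject with arterial access and an attempted introduction into the ITT set. In the 30-day column of SAP Table 2, the MAE-free count k is: "No. of subjects who have been in study for at least 1 day and without an MAE". SAP 8.5 applies the same table to mortality.

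**The concern.** For the first two groups the end of follow-up is tied to the 1-month follow-up, and the protocol accepts that visit halfway through the primary safety window. An implanted subject seen early loses nothing: the 6-month visit follows, and an event from Days 16-30 can still be entered by its onset date. A non-implanted subject has no later study visit and after exit is cared for outside the study.

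The SAP then hides the gap. With one day in study as the only condition, a subject last seen on Day 15 enters the denominator as a full 30-day non-event. Missing an event can only reduce the numerator, so the error has one direction. It affects the primary safety rate and, through SAP 8.5, 30-day mortality. Paraplegia is a further difficulty: Appendix L.2 requires it to persist for more than a month, which cannot be established at a Day-15 exit.

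**Working it through.** **Inputs**

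| Item | Value | Source |
|---|---|---|
| Endpoint window | Days 0-30 inclusive | Protocol H.1, SAP 8.1 |
| 1-month visit | Day 15 to Day 45, target Day 30 | Protocol Table F-1 |
| Minimum time in study for 30-day k | 1 day | SAP Table 2 |
| Planned sample and assumed MAEs | 40 subjects, 2 MAEs (5%) | Protocol C.7, SAP 3.2 |
| Interval | one-sided 95%, binomial | Protocol H.1, SAP 8.4 |
| Number of non-implanted subjects | not given | - |

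**1. The plan's own precision figure.** For x events in n subjects the exact (Clopper-Pearson) one-sided 95% upper limit is U = Beta⁻¹(0.95; x + 1, n − x). For 2/40, U = Beta⁻¹(0.95; 3, 38) = 14.92%, and 14.92 − 5.00 = 9.92 points. The stated margin below 10% is reproduced.

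**2. Unobserved time, worst case.** Exit on Day 15 leaves Days 16 to 30, which is 15 days. That is 15/30 = 50% of the post-operative days, or 15/31 = 48.4% if Day 0 is counted. If the visit falls on Day 30 or later, or if the phrase in F.2.1.2 means target Day 30, the gap is zero.

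**3. Does anything else recover those days?**

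- Later visits: none for non-implanted subjects.
- Timing of the regulatory analysis (H.1, SAP 8.4): it waits until 40 subjects have had the device implanted for 30 days. This protects implanted subjects only.
- SAP Table 2: the minimum times for k are 1, 91 and 305 days. These are the opening days of the imaging windows in SAP Table 1, so the 30-day column in effect requires no follow-up.

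**4. Share of all primary-window time.** With f such subjects among 40, all leaving on Day 15 (both assumed), the share is 15f/(40 × 31):

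- f = 1: 15/1240 = 1.2%
- f = 2: 30/1240 = 2.4%
- f = 4: 60/1240 = 4.8%

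**5. Effect of missed events.** One event in 40 is 1/40 = 2.5 points.

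| True result | Rate | Upper limit | Limit minus rate |
|---|---|---|---|
| 2/40 | 5.0% | 14.9% | 9.9 points |
| 3/40 | 7.5% | 18.3% | 10.8 points |
| 4/40 | 10.0% | 21.4% | 11.4 points |

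If one MAE goes unseen, the second row is reported as the first. If two go unseen, the third is.

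**6. Expected size.** The expected downward bias is f × r × s / 40, where r is the 30-day MAE risk in these subjects and s is the share of that risk falling in Days 16-30. The documents give none of the three. At the low end (f = 1, r = 5%, s = 10%), 1 × 0.05 × 0.10 / 40 = 0.01 points. At the high end (f = 4, r = 40%, s = 50%), 4 × 0.40 × 0.50 / 40 = 2.0 points.

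**7. Effect of a stricter k.** Suppose there are 2 MAEs and f subjects with unknown Day-30 status are left out. For f = 1 the rate is 2/39 = 5.1% (upper limit 15.3%). For f = 2 it is 2/38 = 5.3% (15.7%).

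**The case against.** Exit on Day 15 may not be the intended reading. The Synopsis and C.5 list the first follow-up time point as 1 month after the procedure, F.2.3 speaks of 30 days, and Table F-1 targets Day 30. On that reading F.2.1.2 leaves no gap, and only the looser wording of F.1 combined with the visit window is ambiguous. This stands as a reason to call the point an ambiguity and the 15 days a worst case. It does not remove the point, because no section sets Day 30 as a minimum, whereas the secondary-conversion rule does count days explicitly.

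A reader might infer several stronger things that the documents do not support:

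- *That primary conversions fall into the same gap.* Their rule is a duration of one month, not a visit, and H.1 equates one month with 30 days. What remains is smaller: no contact on or after Day 30 is specified for them.
- *That these are the subjects at highest risk.* This is plausible, but the documents give no MAE rate for failed implants. Some MAE components also arise early: blood loss is counted only in the operating room, and ventilation beyond 24 hours is an early post-operative event. Half of the days need not be half of the risk.
- *That a missed event pushes the trial past a 10% limit.* That figure is a planning precision at an assumed 2/40. The trial is descriptive and has no success criterion, so crossing it decides nothing.
- *That every death within 30 days is classed as aneurysm-related.* L.2 makes this a presumption that evidence can overturn, with final adjudication by the CEC.

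It is also fair to say that rewording alone comes late. Enrollment ended at 69 and this protocol version dates from July 2019, so the exits in question are probably past, though no last-implant date is given. That shifts the weight of the remedy to the counting rule and a site query.

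**Conclusion.** The concern holds for subjects enrolled but not implanted, including treatment failures. A permissible reading of F.1 and F.2.1.2 ends their observation up to 15 days before the primary safety window closes. SAP Table 2 then records them as MAE-free for the whole window. The resulting bias in the 30-day MAE and mortality rates can only be downward.

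Its size is unknown and may be zero, because the documents do not say how many such subjects there were or when they were last seen. Under the assumptions shown, the expected effect is between 0.01 and 2.0 points, and each MAE actually missed costs 2.5 points at N = 40. The point does not show that any event was missed. It is worth correcting because the primary result rests on very few events and the remedy is cheap.

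**What to change.** - **Protocol F.1 and F.2.1.2:** reconcile the exit wording with the Day 0-30 endpoint, so that MAE and vital status through Day 30 are recorded before the exit form is completed. This concerns data for the endpoint; it proposes no change to clinical care.
- **SAP Table 2, 30-day column:** count a subject in k only if status is known through Day 30. Report how many subjects have incomplete 30-day status, and flag any loss of motor function whose persistence could not be established.
- **Sensitivity analysis:** repeat the 30-day MAE rate with every subject of incomplete status counted as having an MAE. With 2 observed MAEs and one such subject this gives 3/40; with two it gives 4/40.
- **Subjects already enrolled:** where consent and local law permit, query sites for MAE and vital status through Day 30 for any non-implanted or converted subject last seen before Day 30. Then rerun the primary table for the 40. The remaining 69 − 40 = 29 subjects affect only later summaries.

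The cost is a few record queries, short wording changes in the protocol and SAP, and possibly a slightly less favourable MAE rate.

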- Adverse events with a possible, probable or causal relationship to the index procedure
- Adverse events leading to subject's death

Secondary procedures performed as a result of any of the above adverse events must be reported on the respective Adverse Event form. Please see guidance for reporting of adverse events following image review in Appendix L.5.

All adverse events that meet the study definitions will be reported to the sponsor and documented on the Adverse Event eCRF and in the subject's medical records.

Clinical events that are inherent to a surgical procedure and expected to occur in the majority of subjects for a projected duration may be considered unavoidable. Such events include, but are not limited to, those listed in Table F-3. These events should not be reported as adverse events during this study.

Table F-3: Expected and un-reportable adverse events related to a surgical procedure

Description of the Event	Time Frame from the Index Procedure
Endoleaks observed and resolved during the index procedure	Resolved by the time the subject leaves the OR
Anesthesia-related nausea and/or vomiting	Within 24 hours
Low-grade fever (< 100° F or < 37.8° C)	Within 48 hours
Back pain related to laying on OR table	Within 72 hours
Incisional pain (pain at access site)	Within 72 hours
Sleep problems, insomnia or post procedural delirium	Within 72 hours
Mild to moderate or bruising or ecchymosis	Within 168 hours

F.6.1 Definitions / Classifications

Adverse Event (AE): (ISO14155:2011 3.2)

Any untoward medical occurrence, unintended disease or injury, or untoward clinical signs (including abnormal laboratory findings) in subjects, users or other persons, whether or not related to the investigational medical device.

NOTE 1: This definition includes events related to the investigational medical device.

NOTE 2: This definition includes events related to the procedures involved.

NOTE 3: For users or other persons, this definition is restricted to events related to investigational medical devices.

Adverse Device Effect (ADE): (ISO14155:2011 3.1)

Adverse event related to the use of an investigational medical device.

NOTE 1: This definition includes adverse events resulting from insufficient or inadequate instructions for use, deployment, implantation, installation, or operation, or any malfunction of the investigational medical device.

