NOTE 2: This definition includes any event resulting from use error or from intentional misuse of the investigational medical device.

Serious Adverse Event (SAE): (ISO 14155:2011 3.37)

Adverse event that

- a) led to death,
- b) led to serious deterioration in the health of the subject, that either resulted in
 - 1) a life-threatening illness or injury, or
 - 2) a permanent impairment of a body structure or a body function, or
 - 3) in-patient or prolonged hospitalization, or
 - 4) medical or surgical intervention to prevent life-threatening illness or injury or permanent impairment to a body structure or a body function,
- c) led to fetal distress, fetal death or a congenital abnormality or birth defect.

NOTE: Planned hospitalization for a pre-existing condition, or a procedure required by the CIP, without serious deterioration in health, is not considered a serious adverse event.

Serious Adverse Device Effect (SADE): (ISO 14155:2011 3.36)

Adverse device effect that has resulted in any of the consequences characteristic of a Serious Adverse Event.

Unanticipated Serious Adverse Device Effect (USADE): (ISO 14155:2011 3.42)

Serious adverse device effect which by its nature, incidence, severity or outcome has not been identified in the current version of the risk analysis report.

NOTE: Anticipated serious adverse device effect (ASADE) is an effect which by its nature, incidence, severity or outcome has been identified in the risk analysis report.

Device deficiency: (ISO 14155:2011 3.15)

Inadequacy of a medical device with respect to its identity, quality, durability, reliability, safety or performance.

NOTE: Device deficiencies include malfunctions, use errors, and inadequate labelling.

F.6.2 Recording and reporting of Adverse Events

Adverse Event (AE) information will be collected throughout the study and reported to Medtronic on the Adverse Event eCRF. The investigator is responsible for reporting all AEs as reportable/collectable per CIP to Medtronic. See the Adverse Event eCRF for the information to be reported for each Adverse Event. Please see guidance for reporting of Adverse Events following image review in Appendix L.5.

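### Table F-3 bars reporting of listed early events with no exception for serious ones, which conflicts with the SAE rules that feed the 30-day SAE endpoint

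*Protocol*

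**What the plan says.** Protocol F.6 sets aside clinical events that are inherent to surgery and "expected to occur in the majority of subjects for a projected duration may be considered unavoidable". Table F-3 gives examples, and the rule for them is "These events should not be reported as adverse events during this study".

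The rows that matter here are:

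- "Anesthesia-related nausea and/or vomiting", within 24 hours
- back pain from the operating table and incisional pain, each within 72 hours
- "Sleep problems, insomnia or post procedural delirium", within 72 hours

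These rows have a time frame, and some name a cause, but none has a severity or seriousness limit. Two other rows do carry a severity limit: fever must be low-grade (below 37.8 °C), and the bruising row reads "Mild to moderate or bruising or ecchymosis".

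F.6.1 defines an SAE as an adverse event that, among other routes, "led to serious deterioration in the health of the subject, that either resulted in" one of several outcomes, including "in-patient or prolonged hospitalization". Table F-4 gives the investigator at most 3 calendar days to report any SAE. F.6.2 limits the investigator's duty to adverse events that the plan itself makes reportable.

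Protocol C.2.2 and SAP Section 5 list "Serious adverse events within 30, 183 and 365 days" as a secondary endpoint. SAP 8.5 computes the rate by the method of SAP Table 2.

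**The concern.** Take a subject with delirium on day 2 that seriously worsens health and prolongs the stay. Table F-3 tells the site not to report it. F.6.1 and Table F-4 tell the site to report it within 3 days. No sentence ranks the two instructions, so each site must choose.

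The SAE endpoint is built from reported events. A site that follows Table F-3 removes a qualifying SAE from the count, and nothing in the conflict can add one, so the error runs in one direction and makes the early safety profile look better. The DMC, whose task under I.2.2 is to evaluate the safety data, would also not see the event through adverse event reporting.

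**Working it through.** **1. The plan's own figure.** The only computed precision figure is in Protocol C.7 and SAP 3.2: for 2 MAEs in 40 subjects (5%), the one-sided 95% upper limit lies less than 10 points above the estimate. The exact binomial upper limit is the 0.95 quantile of Beta(3, 38), which is 14.92%; 14.92 − 5 = 9.92 points. The figure reproduces. It concerns the primary MAE rate, and this point does not affect it.

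**2. Search for an exception.** I read Protocol F.6, Table F-3, F.6.1, F.6.2, Table F-4, C.2.2 and H.1, and SAP Sections 5, 8.4 and 8.5, for any statement that a Table F-3 event meeting the SAE definition must still be reported. There is none.

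| Place | Effect on a serious Table F-3 event |
|---|---|
| F.6 and Table F-3 | Not reported; no seriousness test |
| F.6, sentence on events meeting the study definitions | Reported; Table F-3 not mentioned |
| F.6.1 | Is an SAE if deterioration is serious and the stay is prolonged |
| F.6.2 | Duty covers what the plan makes reportable, which leads back to F.6 and Table F-3 |
| Table F-4 | SAE due within 3 calendar days; Table F-3 not mentioned |

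**3. Does the timing fall inside the endpoint?** H.1 and SAP 8.1 define events within 30 days as Day 0 to Day 30 inclusive. The longest Table F-3 time frame is 168 hours, or 168/24 = 7 days, so every row lies inside the 30-day window.

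**4. Effect per subject.** Under SAP Table 2 the rate is m/(m + k). A subject whose only SAE in the window goes unreported moves from m to k, and the denominator is unchanged if all subjects are evaluable.

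- Regulatory set: 1/40 = 2.5 percentage points
- All enrolled: 1/69 = 1.45 percentage points

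A subject with another reported SAE in the window is already in m, and the rate does not change.

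**5. Range under assumption.** The documents give no frequency. Let p be the assumed proportion of subjects whose sole 30-day SAE is a Table F-3 event that goes unreported. The expected number omitted is N × p, and the chance of at least one is 1 − (1 − p)^N.

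| Assumed p | Expected of 40 | At least one of 40 | Expected of 69 | At least one of 69 |
|---|---|---|---|---|
| 1% | 0.4 | 33% | 0.7 | 50% |
| 2% | 0.8 | 55% | 1.4 | 75% |
| 5% | 2.0 | 87% | 3.5 | 97% |
| 10% | 4.0 | 98% | 6.9 | 99.9% |

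The table shows how sensitive the count is to p. It does not estimate p.

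**The case against.** The strongest reply is that the bar is not unconditional. The paragraph concerns events expected in most subjects and treated as unavoidable, and an event with serious deterioration fits that description poorly. The preceding sentence in F.6 has all events meeting the study definitions reported, and Table F-4 has no exception. A careful site could well report. This stands in part: it makes inconsistent capture between sites as plausible as uniform omission. It does not remove the conflict, because the events are listed by name without a limit and no precedence is stated.

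The time column can also be read to mean that an event persisting past its limit leaves the table, which narrows the group. An event that settles inside the limit can still have prolonged the stay.

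It is also true that the endpoint is secondary and descriptive, that no Table F-3 event is a component of the primary MAE endpoint, that the adverse event eCRF and safety plan are not available to show how sites were instructed in practice, and that enrollment ended at 69. A wording change alone would alter no future report, since every time frame in the table has closed.

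A reader might infer more than the documents support:

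- **That strokes are lost.** Stroke has its own definition in Appendix L.2, is not in Table F-3, and goes to CEC adjudication. Adverse event assessment is repeated at discharge and 1 month. A stroke first taken for delirium is reportable once recognised; one never recognised is not a product of Table F-3.
- **That the 183- and 365-day rates inherit the loss.** SAP 8.5 applies Table 2, which counts onset from Day 31 to 183 and from Day 184 to 365, so early events do not enter those numerators. H.1 and SAP 8.1 define within 365 days as Day 0 to 365, and the two are not reconciled. The documents therefore do not establish an effect on the later rates.
- **That delirium fails the majority test and should leave the table.** The documents give no delirium rate, so this cannot be shown from them.

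**Conclusion.** The conflict is real and no text in either document resolves it. Its effect is confined to the descriptive 30-day SAE rate and can only lower it: 2.5 points per affected subject at N = 40, 1.45 points at N = 69.

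This rests on three conditions: a listed event met the full SAE definition (serious deterioration as well as a qualifying outcome), the site followed Table F-3, and the subject had no other reported SAE by Day 30. How often they coincide is unknown, so the size of any bias is unknown and may be zero. The documents support a risk of omission or uneven capture. They do not show that SAEs were in fact left out. With so few subjects, one or two cases would visibly change the reported rate, which makes the point worth settling before the SAE rate is interpreted.

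**What to change.** 1. **Reconcile the passages.** Add to F.6, above Table F-3, that a listed event is reportable whenever it meets the SAE, ADE or MAE definition. The table itself can stay as it is.
2. **Recover past events.** Before looking at the data, fix a cut-off for ICU time and for hospital stay. Both are already collected: ICU hours at discharge (Protocol F.2.2), and hospital days from the index procedure to discharge (SAP Section 5). Send one query for each subject above either cut-off, asking whether a Table F-3 event met the SAE definition. Add any that did to the 30-day SAE count.
3. **If the query is not done,** state in the report that the SAE rates may exclude Table F-3 events whatever their seriousness.

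The cost is one sentence and a few data queries. With in-person monitoring replaced by telephone and email (G.2), sites would have to answer these from their own records. The SAE rate may become slightly less favourable.
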